## 1.0 Research Introduction

### 1.1 Purpose/Specific Aims

#### 1.1.1 Objectives:

##### **Primary Objectives**

- The primary objective of this study is to determine the safety of trigriluzole in combination with PD-1 inhibiting antibodies, and to define a maximum tolerated dose (MTD) of trigriluzole in combination therapy.

##### **Secondary Objectives**

- To characterize the efficacy of the combination therapy.
- To identify markers of response to trigriluzole in the tumor microenvironment.

#### 1.1.2 Hypotheses:

##### **Primary Hypotheses**

- Combination treatment with trigriluzole + PD-1 inhibitor will have a tolerable adverse event profile.

##### **Secondary Hypothesis/Hypotheses**

- The combination therapy will induce tumor regression.
- Features in the tumor microenvironment (TME) may predict response to therapy.

#### 1.1.3 Endpoints:

##### **Primary Endpoint**

- The primary endpoint is the MTD/RP2D. Data on the adverse event type, severity and frequency will be recorded.

##### **Secondary Endpoints**

- objective response rate (ORR)
- adverse event type, severity and frequency

Protocol Number: RCINJ# 051707

PI Name: [name]

Protocol Title: A Phase I Study to Evaluate the Safety of Trigriluzole (FC-4157/BHV-4157) in Combination with PD-1 Blocking Antibodies

4

RESERVED FOR IRB STAMP  
DO NOT MODIFY THIS SPACE

Form Version v120116

**RUTGERS | eIRB**  
**APPROVED**

IRB ID: Pro20170000453  
Approval Date: 10/4/2019  
Expiration Date: 4/3/2020

- survival time (OS), landmark survival rates at 1 and 2 years
- duration of response for responding patients
- time to progressive disease (PFS)
- time to treatment failure
- time to next therapy or death (TTNTD)
- freedom from new metastases

**Correlative science endpoints: changes in the tumor microenvironment and peripheral blood in the following categories:**

- TILs and PD-L1 expression
- Immune cell phenotypes and gene expression
- Angiogenesis markers
- Metabolic effector molecules
- Exosomal formation

## 1.2 Research Significance

GRM1 is a metabotropic glutamate receptor, which is expressed on 60-80% of melanomas and numerous other cancer types. GRM1 signal transduction results in a number of downstream effects mainly through activation of the MAPK and PI3k/AKT pathways. These effects include increased tumor growth, increased tumor angiogenesis, increase in tumor-derived exosome production, and decreased tumor apoptosis. We have confirmed these findings using specimens from patients with advanced melanoma who participated on clinical trials using the GRM1-blocking agent riluzole.

Recently, we found that another effect of GRM1 signal transduction is suppression of tumor in the microenvironment. GRM1 signal transduction increases the expression of CCL4 and M-CSF in the tumor microenvironment *in vivo*, an effect that is likely mediated through tumor-derived exosome biogenesis and release. Conversely, inhibiting GRM1 signal transduction results in a decrease in the numbers of M2-type (suppressive) tumor-associated macrophages (TAMs), myeloid-derived suppressor cells (MDSCs) and regulatory T cells (T regs), and an increase in the numbers of tumor-infiltrating lymphocytes (TILs).

Response to immune checkpoint agents is more frequent in patients with tumors containing TILs and other markers of a so-called “hot” tumor. Agents such as riluzole or its pro-drug trigriluzole could therefore be used to convert a “cold” tumor into a “hot” tumor, priming the

Protocol Number: RCINJ# 051707

PI Name: [name]

Protocol Title: A Phase I Study to Evaluate  
the Safety of Trigriluzole (FC-4157/BHV-  
4157) in Combination with PD-1 Blocking  
Antibodies

5

RESERVED FOR IRB STAMP  
DO NOT MODIFY THIS SPACE

Form Version v120116

IRB ID: Pro20170000453  
Approval Date: 10/4/2019  
Expiration Date: 4/3/2020

**RUTGERS | eIRB**  
**APPROVED**

tumor to respond to anti-PD-1 immune checkpoint antibodies. The primary objective of this study is therefore to determine the safety of trigriluzole in combination with PD-1 inhibiting antibodies, and to define a MTD of this agent in combination with PD-1 inhibiting antibodies for use in future combinatorial studies.

### **1.3 Research Design and Methods**

**All visits are relative to the treatment start date, Day -14. If a treatment visit is delayed, the next visit will still occur on time relative to the initial start date (e.g. If Week 3 occurs 7 days late, Week 5 will still occur at Week 5).**

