##### **Anti-PD-1 antibody (pembrolizumab or nivolumab)**

PD-1 inhibitor treatment will consist of either nivolumab or pembrolizumab. PD-1 inhibitor will begin at Week 1 (following 14 day lead-in with trigriluzole). Subsequent PD-1 inhibitor treatments will occur at 2-3-week intervals, depending on the schedule of the PD-1 inhibitor as per the Study Calendar.

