#### **Nivolumab or Pembrolizumab Administration**

Nivolumab or pembrolizumab will be administered in the outpatient setting.

Nivolumab will be administered at the FDA-approved dose and schedule of 240 mg IV Q2 weeks over 60 minutes.

Pembrolizumab will be administered at the FDA-approved dose and schedule of 200 mg IV Q3 weeks over 30 minutes.

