## 1.10 Timetable/Schedule of Events

### Schema

#### Trigriluzole + Nivolumab

#### Trigriluzole + Pembrolizumab

**Trigriluzole + Nivolumab Study Calendar**

	Screening/ Baseline 	Treatment Week									
		Week -2	Week -1	Week 1	Week 3	Week 5	Week 7	Week 9	Q2 weeks (Weeks 11 – 109)	Q4 weeks  (Weeks 13 – 109)	Weeks 13, 25, 37, 49
Scheduling Window (Days):		Within 14 d	±3	±1	±7	±7	±7	±7	±7	±7	±7
Informed Consent	X										
Inclusion/Exclusion Criteria	X										
Demographics and Medical History, including BRAF status	X										
Prior and Concomitant Medication Review	X	X	X	X	X	X	X	X	X	X	X
Assess Baseline Symptoms/Adverse Events and Compliance	X	X	X	X	X	X	X	X	X	X	X
Vital Signs and Weight	X	X	X	X	X	X	X	X	X	X	X
ECOG Performance Status, Physical Examination	X	X		X	X	X	X	X		X	X
Routine Safety Laboratory Studies 	X	X 		X	X	X	X	X		X	X
Serum GGT	X			X			X				X
ECG 		X	X	X			X				X 
Trigriluzole Administration (PO continuous dosing)		X	X	X	X	X	X	X	X	X	X
Nivolumab Administration				X	X	X	X	X	X	X	X
Research Blood Collection for PK 		X		X			X				
Research Blood Collection for correlative science 	X			X			X				X 
Tumor Tissue Collection 	X			X			X				
Tumor Assessment 	X						X				X

Protocol Number: RCINJ# 051707

PI Name: [name]

Protocol Title: A Phase I Study to Evaluate the Safety of Trigriluzole (FC-4157/BHV-4157) in Combination with PD-1 Blocking Antibodies

47

RESERVED FOR IRB STAMP  
DO NOT MODIFY THIS SPACE

Form Version v120116

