### **DLT observation period**

There will be a 5-week evaluation period for observation of DLT during which time new subjects may be accrued within the same dose cohort, but dose escalation or de-escalation beyond the current dose cohort shall not be allowed. The date of reference for the 5 weeks is the first day of treatment including the lead-in period (Day -14); therefore the end of the DLT observation period occurs at Week 3. The end of the DLT observation period will not coincide with an office visit in the pembrolizumab cohorts; if no DLT has been reported by that time, the evaluation period will be considered to be passed.

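### Fixed-date visits with ±7-day windows allow PD-1 infusions closer together than the stated Q2- and Q3-week schedules, and compliant subjects can differ in the number of infusions inside the DLT period

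*Combined protocol and SAP*

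**What the plan says.** **Visit anchor.** Section 1.3 states "All visits are relative to the treatment start date, Day -14" and "If a treatment visit is delayed, the next visit will still occur on time relative to the initial start date". It illustrates this with "If Week 3 occurs 7 days late, Week 5 will still occur at Week 5".

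**Windows.** In the calendars of section 1.10, Week 1 has ±1 day. Every later nivolumab visit (Weeks 3, 5, 7, 9 and onward) and every later pembrolizumab visit (Weeks 4, 7 and onward) has ±7 days. The infusion is marked on these same visits and has no window of its own.

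**Infusion schedule.** Section 1.7.6: "Nivolumab will be administered at the FDA-approved dose and schedule of 240 mg IV Q2 weeks over 60 minutes" and "Pembrolizumab will be administered at the FDA-approved dose and schedule of 200 mg IV Q3 weeks over 30 minutes". Tables 3 and 4 repeat the two- and three-week schedules. Section 1.7.5.1 adds "Subsequent PD-1 inhibitor treatments will occur at 2-3-week intervals". No section gives a minimum interval between infusions.

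**Late and missed doses.** Under section 1.7.7, doses lost to an interruption are left out rather than given late, and PD-1 doses held for toxicity are skipped. The same section accepts delays for holidays, weekends and weather, followed by a return to the original timetable.

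**DLT period.** Treatment Assignment (section 1.7.5) and the Definition of DLT (section 6.1) use 4 weeks. The DLT observation period text in section 6.1 uses 5 weeks from Day -14: "therefore the end of the DLT observation period occurs at Week 3".

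**Evaluability.** Section 6.1 treats a subject as evaluable for toxicity after at least one dose of each drug. It replaces those not evaluable over the whole DLT period, up to 5.

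**The concern.** The PD-1 antibody is meant to be the constant background against which the trigriluzole dose is escalated. Two features of the timetable loosen that.

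First, a late infusion followed by an on-time one shortens the interval below the stated schedule, and section 1.3 presents this as the rule working as intended.

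Second, the ± sign also permits early visits, so the amount of PD-1 antibody given before the DLT assessment closes can differ between subjects who all comply.

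The second feature bears on the primary endpoint. The DLT definition counts related Grade 3 or higher toxicity from either drug or the combination. In Table 6, with three subjects at a dose, no DLT means escalate and one means stay, so a single event changes the decision. Subjects with one infusion and subjects with two enter that table as equivalent, and the evaluability text does not distinguish them.

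**Working it through.** **1. Day numbering.** Section 1.7.6 says there is no Day 0, so the lead-in is Days -14 to -1 (14 days) and Week w starts on Day 7(w − 1) + 1.

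| Visit | Nominal day | Window | Allowed days |
|---|---|---|---|
| Week 1 (both) | 1 | ±1 | -1 to 2 |
| Week 3 (nivolumab) | 15 | ±7 | 8 to 22 |
| Week 4 (pembrolizumab) | 22 | ±7 | 15 to 29 |
| Week 5 (nivolumab) | 29 | ±7 | 22 to 36 |
| Week 7 (both) | 43 | ±7 | 36 to 50 |

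**2. The plan's own figure.** Five weeks from Day -14 is 35 days, and 35 − 14 = 21. The period ends on Day 21, the last day of Week 3, which agrees with section 6.1. Four weeks is 28 days, and 28 − 14 = 14. That period ends on Day 14, the day before the nominal Week 3 visit.

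**3. The section 1.3 example.**
- Nivolumab: Week 3 seven days late is Day 15 + 7 = 22. Week 5 on time is Day 29. Interval 29 − 22 = 7 days, against 14.
- Pembrolizumab, same pattern: Week 4 seven days late is Day 22 + 7 = 29. Week 7 on time is Day 43. Interval 43 − 29 = 14 days, against 21.

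**4. Early Week 3 visit.** The earliest allowed day is 15 − 7 = 8. With Week 1 on Day 1 the interval is 7 days; with Week 1 on Day 2 it is 6. At the other end, Week 1 on Day -1 and Week 3 on Day 22 gives 22 days. The first nivolumab interval can therefore run from 6 to 22 days.

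**5. Infusions inside the DLT period.**

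| Antibody and period | On schedule | Alternative within windows |
|---|---|---|
| Nivolumab, 4 weeks (to Day 14) | 1 | 2 if Week 3 is on Days 8–14 |
| Nivolumab, 5 weeks (to Day 21) | 2 | 1 only if Week 3 is on Day 22 |
| Pembrolizumab, 4 weeks | 1 | none |
| Pembrolizumab, 5 weeks | 1 | 2 if Week 4 is on Days 15–21 |

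If the period is instead taken to end at the nominal Week 3 visit (Day 15 inclusive), nivolumab gives 2 on schedule and 1 if Week 3 is on Days 16–22.

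**6. Sensitivity to the last day.** If Day 22 were counted as inside the 5 weeks, a late Week 3 visit would no longer lower the nivolumab count. For pembrolizumab the count would be 2 on schedule and 1 if Week 4 is on Days 23–29. Section 6.1 says the end of the period does not coincide with a pembrolizumab visit. That favours Day 21, because Day 22 is the nominal Week 4 visit.

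**The case against.** A window around a nominal date is ordinary practice, and anchoring to the start date prevents drift. In the section 1.3 example the infusions fall on Days 1, 22 and 29: three by Day 29, the same number as on schedule, with a 21-day gap before the 7-day one. Section 1.7.7 already omits missed doses and skips toxicity-held ones. It explains the return to timetable as a way of keeping assessments comparable between subjects. For pembrolizumab, the background in section 1.4.7 describes study at two- to three-week intervals, so 14 days lies within what the document reports.

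Most of this stands as a defence of anchored assessments. It does not settle infusion spacing. A visit given late but inside its window is neither a missed dose nor a toxicity hold, and section 1.7.7 itself permits some delays followed by a return to the fixed dates. If the omit and skip rules were meant to bar late infusions, the section 1.3 example conflicts with them.

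Four stronger readings are tempting, and the documents do not support them:
- **Two nivolumab infusions 0 days apart.** This needs Week 3 at +7 and Week 5 at -7, both on Day 22. Section 1.3 says that after a delay "If a treatment visit is delayed, the next visit will still occur on time relative to the initial start date", so the floor after a late visit is 7 days. A 7-day pembrolizumab gap relies on the same pairing of opposite window ends.
- **The section 1.3 example distorts the MTD.** Its shortened interval runs from Day 22 to Day 29, after the 5-week DLT period has closed on Day 21. Compression inside the period comes only from an early visit.
- **Subjects routinely receive different numbers of infusions.** On the nominal schedule, everyone on the same antibody receives the same number. On the 5-week reading, the nivolumab count changes on one day of a 15-day window.
- **Shorter gaps add toxicity.** Nothing in the documents shows this.

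**Conclusion.** The concern holds on two separate counts. First, the visit rule in section 1.3, followed exactly, gives a 7-day nivolumab interval against a two-week schedule and a 14-day pembrolizumab interval against a three-week one, with no stated minimum. Second, the ± window lets compliant subjects reach the end of the DLT period with different PD-1 exposure: 1 or 2 infusions for nivolumab on either stated length, and 1 or 2 for pembrolizumab on the 5-week length. The variation is widest for nivolumab on the 4-week reading and for pembrolizumab on the 5-week reading (seven of the 15 allowed days in each). It is narrowest for nivolumab on the 5-week reading (one of 15).

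This rests on the calendar windows applying to the infusion as well as the visit, since no other window is given, and on Day 21 as the last day of the 5 weeks. How often visits would fall at these edges is not known, so the size and direction of any effect on the MTD cannot be stated. The problem is an inconsistency between stated rules, and the sponsor should resolve it before the dose decisions rely on them.

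**What to change.** 1. Reconcile section 1.3, the Anti-PD-1 antibody text in section 1.7.5.1, Tables 3 and 4, sections 1.7.6 and 1.7.7 (including the PD-1 dose modification text), and both calendars in section 1.10, on infusion spacing and on what happens when a visit is late.
2. Keep assessment visits anchored to Day -14, but give infusions a window of their own. The sponsor should state the shortest permitted interval for each antibody and what happens to an infusion that would break it.
3. Reconcile the 4-week and 5-week DLT periods in Treatment Assignment, Definition of DLT and DLT observation period, and name the last day.
4. In the evaluability and missing-data text of section 6.1, state what PD-1 exposure within that period a subject needs to be counted as DLT-free.

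All values are for the sponsor to set. The change is protocol wording and two calendar rows, with no added procedures. The downside is that some late or early infusions would be moved or omitted, and a few subjects may need replacing within the existing allowance of 5.

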#### **1.3.1 Overview**

In the first portion of this study, cohorts of subjects will be treated with increasing doses of trigriluzole in combination with nivolumab. After the MTD of trigriluzole is identified, it will be tested in combination with pembrolizumab. The MTD of trigriluzole with nivolumab is likely to be safe and tolerable with pembrolizumab. The sequential design is justified because nivolumab and pembrolizumab are both PD-1-blocking antibodies and there are no discernible differences in the safety profiles. Thus, the data obtained from the pembrolizumab group are not independent of the data in the nivolumab treatment group. The sequential design limits the size and the cost of the trial.

#### **1.3.2 Duration of Study**

Subjects will remain on the active treatment phase of the study until confirmed disease progression, unacceptable toxicity, or withdrawal of consent, up to a maximum treatment duration of 109 weeks. The entire study is expected to take 2 years to complete. Patients who have derived clinical benefit from study treatment may have access to trigriluzole through a separate continuation trial (rollover trial).

#### **1.3.3 Screening period/Baseline**

Screening evaluations must be performed no more than 28 days prior to registration. The subject must begin study treatment no more than 14 days after registration. Baseline research blood and tumor samples may be performed anytime prior to the start of therapy. Ideally, the research blood samples should be collected 3-14 days prior to the tumor biopsy, but it is also acceptable to collect them on the same day.

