### **Blood sampling for correlative studies**

- Research blood collection for correlative studies is to be performed at Baseline/Week -2 (anytime pre-treatment), Week 1 (pre-infusion, untimed sample), Week 7 (pre-infusion, untimed sample), and Week 13 (pre-infusion, untimed sample).
- At Baseline, 1 green top tube and 1 red top tube will be collected.
- At Week 1, 1 green top tube and 1 red top tube will be collected.
- At Week 7, 1 green top tube and 1 red top tube will be collected.
- At Week 13, 1 green top tube and 1 red top tube will be collected.
- Refer to the Lab Manual for details on collection, processing and storage.

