**RUTGERS | eIRB**  
**APPROVED**

IRB ID: Pro20170000453  
Approval Date: 10/4/2019  
Expiration Date: 4/3/2020

Footnotes

1. Screening evaluations must be performed no more than 28 days prior to registration. The subject must begin study treatment no more than 14 days after registration.
2. Routine safety labs: CBC with Differential, Comprehensive Metabolic Panel, Amylase, Lipase, TSH, Free T4, LDH. Routine safety labs do not need to be repeated on Week -2 if performed in the past 14 days. More frequent labs may be performed as clinically necessary, as determined by treating investigator. WOCBP must have a negative serum beta-HCG pregnancy test prior to the first dose. During study treatment, pregnancy testing may be performed as indicated at the treating physician's discretion.
3. ECG monitoring is to be performed at the following treatment visits: a) at baseline (prior to dose on start date Week -2), and at expected  $C_{max}$  4 hours post trigriluzole (window  $\pm$  30 minutes), b) at steady state on Week -1 and c) at steady state at Week 1 (untimed), d) at steady state at weeks 7, 13, 25, 37, and 49. If trigriluzole has been discontinued, EKG monitoring may be discontinued.
4. Research blood collection for PK analysis is to be performed at the following treatment visits: a) start date (Week -2) at pre-treatment, and at 2 hours and 4 hours post trigriluzole (window  $\pm$  30 minutes), b) Week 1 (untimed sample, pre-infusion), and c) Week 7 (untimed sample, pre-infusion). No PK collections after Week 7.
5. Research blood collection for correlative studies is to be performed at Screening/Week -2 (pre-treatment, untimed), Week 1 (pre-infusion, untimed), Week 7 (pre-infusion, untimed), and Week 13 (pre-infusion, untimed). Baseline research blood and tumor samples may be performed anytime prior to the start of therapy. Ideally, the research blood samples should be collected 3-14 days prior to the fresh tumor biopsy, but it is also acceptable to collect them on the same day. No research bloods after Week 13.
6. Tumor Tissue Collection. Archival tissue (a block or 6-10 unstained slides) will be obtained for all subjects, when available. Research biopsies are optional but strongly encouraged at Baseline/Week -2, and Week 1, and Week 7. No biopsies after Week 7.
7. Tumor Assessment must be performed at Screening, Weeks 7, 13, 25, 37, 49, 61, 73, 85, 97, and 109.
8. Q4 weeks starting from Week 13: Weeks 13, 17, 21, 25, 29, 33, 37, 41, 45, 49, etc.

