### **Inclusion Criteria**

A patient/subject is eligible for enrollment if *all* of the following inclusion criteria are met.

- 1) Patients must have histologically confirmed solid malignancy or lymphoma that is metastatic or unresectable
- 2) There is reasonable expectation of response to pembrolizumab or nivolumab, and one of the drugs is available from the commercial supply. This includes (but is not limited to) the following tumor types: melanoma, non-small cell lung cancer, renal cell carcinoma, squamous cell carcinoma of the head and neck, bladder cancer, and classic Hodgkin lymphoma.
- 3) The patient must have failed at least one line of standard treatment, with the following exceptions in which a PD-1 antibody is FDA approved in the first-line setting:
  - a. melanoma patients
  - b. non-small cell lung cancer patients without EGFR or ALK genomic tumor aberrations whose tumors have high PD-L1 expression [(Tumor Proportion Score (TPS)  $\geq 50\%$ )] as determined by an FDA-approved test.
- 4) Age  $\geq 18$  years old
- 5) Patients must give informed consent.
- 6) Prior chemotherapy, immunotherapy, radiotherapy or major surgery (including radiation therapy or surgery for treatment of brain metastases) must be

completed at least 3 weeks before study entry. Prior PD-1 or PD-L1 therapy is acceptable.

- 7) Patients must have an ECOG performance status  $\leq 2$  (Appendix A).
- 8) Patients must have normal organ and marrow function as defined below:
  - a. Hemoglobin  $>8.0$  mg/dL (without transfusion in the preceding 7 days)
  - b. Platelets  $\geq 70,000$  / $\mu$ L
  - c. Total bilirubin within normal institutional limits (patients with Gilbert's Syndrome must have a total bilirubin  $< 3.0$  mg/dL).
  - d. AST(SGOT)  $<2X$  institutional ULN
  - e. ALT(SGPT)  $<2X$  institutional ULN
- 9) Patients must have measurable disease, defined as at least one lesion that can be accurately measured in at least one dimension (longest diameter to be recorded) as  $\geq 10$  mm by CT scan, PET/CT scan, MRI or caliper/ruler measurement by clinical exam. Lymph nodes: to be considered pathologically enlarged and measurable, a lymph node must be  $\geq 15$  mm in short axis when assessed by CT scan. Lesions that have been radiated in the advanced setting cannot be included as sites of measurable disease unless clear tumor progression has been documented in these lesions since the end of radiation therapy.
- 10) Ability to swallow pills

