#### **Exclusion Criteria**

A patient /subject will not be eligible for this study if *any* of the following exclusion criteria are met.

- 1) Systemic immunosuppressive medications such as steroids. The following steroid formulations are permitted: intranasal, intra-articular, and inhaled steroids.
- 2) History of immune-related adverse event from prior immunotherapy treatment that has not improved to grade 0-1. Subjects with grade 2 hypothyroidism and grade 2 adrenal insufficiency requiring continued medical treatment may enroll provided that they are asymptomatic and stable on their dose of hormone replacement.
- 3) Serious concomitant systemic disorders (including active infections) that would compromise the safety of the patient or compromise the patient's ability to complete the study, at the discretion of the investigator, including active autoimmune disease requiring treatment within the past 30 days.
- 4) Any condition requiring systemic treatment with either corticosteroids ( $>10$  mg daily prednisone equivalents) or other systemic immunosuppressive medications within 14 days of study drug administration. Inhaled or topical steroids and adrenal replacement doses  $<10$  mg daily prednisone equivalents are permitted in

the absence of active autoimmune disease. Patients are permitted to use topical, ocular, intra-articular, intranasal, and inhalational corticosteroids (with minimal systemic absorption). Physiologic replacement doses of systemic corticosteroids are permitted, even if <10 mg/day prednisone equivalents. A brief course of corticosteroids for prophylaxis (e.g., contrast dye allergy) or for treatment of non-autoimmune conditions (e.g., delayed-type hypersensitivity reaction caused by contact allergen) is permitted.

- 5) Second primary malignancy, except those second primary malignancies that are not considered to be competing causes of death in the opinion of the treating investigator. Examples include: *in situ* carcinoma of the cervix, adequately treated non-melanoma carcinoma of the skin, or other malignancy treated at least 5 years previously with no evidence of recurrence.

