### **Analysis Plan for Secondary Endpoints**

Clinical Secondary Endpoints. The frequency of AEs and SAEs will be recorded. Clinical measures of efficacy will be described, including overall survival, progression-free survival, etc. (see Secondary Endpoints above). Descriptive statistical will be used, except where otherwise specified. Continuous variables will be presented by summary statistics (such as mean, median, standard error and 90% CI) and the categorical variables by frequency distributions (i.e., frequency counts, percentages and 90% CI).

Correlatives. We will collect pre- and post-treatment tumor samples from responders and non-responders to test for differences in signal transduction in key pathways (MAPK, Pi3K/AKT), presence of TILs and other immune effector cells, PD-L1 expression, the expression of VEGF, IL-8, CD34, CCL2, M-CSF, and immune-related gene expression profile. We will determine if the presence of GRM1 expression, activating mutations in B-RAF or N-RAS, or PTEN inactivation (or activating B-RAF mutations and PTEN inactivation together) in the pre-treatment tumor samples correlates with response to therapy. We will examine the change in key pathways before and after the trigriluzole monotherapy lead-in period (Baseline vs. Week 1) and compare to the samples taken after exposure to combination therapy (Week 7).

We will also collect pre- and post-treatment peripheral blood samples from responders and non-responders and determine the expression of VEGF, IL-8, CD34, CCL2, and M-CSF, and changes in the quantity and contents of tumor-derived exosomes. We will determine if the expression of these markers in pre-treatment peripheral blood samples correlates with response to therapy. Next, we will compare the pre-treatment and post-treatment blood and tumor samples to see if response to treatment correlates with activation or suppression of signal transduction through the MAPK and PI3K/AKT pathways, changes in immune effector cells in the tumors and peripheral blood, or changes in the quantity or contents of peripheral blood exosomes.

Treatment effect for each patient will be measured as paired differences between pre- and post- measurements of these parameters at various times. Transformation of the data will be performed if appropriate, e.g. log transformation, and hence treatment effect will be expressed on a log scale.

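### Baseline research samples have no earliest date and are not tied to the end of prior therapy, so the Baseline vs. Week 1 change can mix off-drug recovery with the trigriluzole effect

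*Combined protocol and SAP*

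**What the plan says.** **Baseline timing.** Section 1.3.3 gives only a latest limit: "Baseline research blood and tumor samples may be performed anytime prior to the start of therapy". Section 1.8 repeats it for tumor sampling and for correlative blood, where the time point is "Baseline/Week -2 (anytime pre-treatment". Footnote 5 of both study calendars (section 1.10) reads "Research blood collection for correlative studies is to be performed at Screening/Week -2 (pre-treatment, untimed" and repeats the section 1.3.3 rule.

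**Neighbouring limits, all anchored elsewhere.**
- Screening tests: "Screening evaluations must be performed no more than 28 days prior to registration".
- First dose: "The subject must begin study treatment no more than 14 days after registration".
- Prior chemotherapy, immunotherapy, radiotherapy or major surgery (inclusion criterion 6): "completed at least 3 weeks before study entry". The enrollment procedures in section 1.3.8 treat registration as the point at which a patient is on study.
- Steroids above 10 mg prednisone equivalent (exclusion criterion 4), together with "other systemic immunosuppressive medications within 14 days of study drug administration". Exclusion criterion 1 also bars systemic immunosuppressants, without saying at what date.
- Baseline tumor measurements (section 1.7.12): no more than 4 weeks before treatment. This covers disease assessment, not research samples.

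**Use of the samples.** The Analysis Plan for Secondary Endpoints (section 6.1) says "We will examine the change in key pathways before and after the trigriluzole monotherapy lead-in period (Baseline vs. Week 1", and compares these with Week 7 samples taken on the combination. A separate general sentence defines each patient's treatment effect as the paired pre/post difference. Neither mentions sample date or time since earlier treatment. The same section calls the correlative work descriptive and concedes that the sample may be too small to test correlations.

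**The concern.** The lead-in exists so that trigriluzole can be seen alone: the Week 1 sample is taken before the first infusion, and every later sample follows PD-1 antibody exposure. A Baseline-to-Week 1 change can be read as a trigriluzole change only if little else happens between the two samples. Under the present rule the baseline sample may be weeks old at first dose, and may date from before chemotherapy, radiotherapy or steroids had stopped or cleared. Recovery of immune cells and signalling would then appear in the same paired difference as the drug. The lag will also differ between patients, which adds variation to a small set of pairs: at most 27 subjects, with research biopsies optional. What is at stake is the secondary objective on markers of response to trigriluzole in the tumor microenvironment (section 1.1.1). The plan also relates the pre-treatment samples to response, so uneven baseline timing affects that comparison too.

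**Working it through.** **1. The plan's own interval.** Day -14 to Day -1 is 14 days, and Day 1 follows directly (section 1.7.6). The stated 14-day lead-in reproduces. The ±1-day window at Week 1 is ignored below.

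**2. Off-drug share of the interval.** Let d be the days from baseline sample to first dose. The interval is d + 14 and the off-drug share is d/(d + 14).

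| d | Interval (days) | Off drug | On drug |
|---|---|---|---|
| 0 (Week -2, pre-dose) | 14 | 0% | 100% |
| 7 | 21 | 33% | 67% |
| 14 | 28 | 50% | 50% |
| 28 | 42 | 67% | 33% |
| 42 (28 + 14) | 56 | 75% | 25% |

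The last row assumes that the 28-day screening limit covers the research sample. That assumption favours the plan. If the untimed wording overrides it, the only earliest bound is signed consent (section 4.1.5).

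**3. Overlap with prior cancer therapy.**
- Study entry = registration: therapy may end 21 days before registration and the sample may be 28 days before it, so the overlap is up to 28 − 21 = 7 days.
- Study entry = first dose: up to 42 − 21 = 21 days.

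**4. Overlap with steroids.** Criterion 4 alone allows up to 42 − 14 = 28 days. The figure is the same if criterion 1 is applied at registration (14 days before first dose). If criterion 1 is applied when the sample is drawn, the overlap is zero. The text does not say which.

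**5. Can the share of the measured change be found?** Not from the documents: they give no recovery time, marker variance or drug effect. As an illustration on assumed inputs, let W be the full recovery shift, δ the trigriluzole effect and h the recovery half-life. Then

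share = W·f / (W·f + δ), with f = 2^(−t0/h) − 2^(−t1/h),

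where t0 and t1 are the days from end of prior therapy to the baseline and Week 1 samples. Assume h = 7, 14 or 28 days.

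Sample at or before the end of therapy: t0 = 0, and t1 = 21 + 14 = 35 or 35 + 14 = 49. Then f runs from 0.580 (t1 = 35, h = 28) to 0.992 (t1 = 49, h = 7).

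| W/δ | Share due to recovery |
|---|---|
| 0.5 | 22–33% |
| 1 | 37–50% |
| 2 | 54–66% |

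The share exceeds one half only if W > δ/f, that is, if W is more than 1.01 to 1.73 times δ.

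**6. The same model with the sample taken after a 21-day washout.** For d = 0 (t0 = 21, t1 = 35), the share is 4–26% over W/δ = 0.5 to 2. For d = 14 (t0 = 21, t1 = 49), it is 6–37%. A window reduces the mixing but does not remove it.

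**The case against.** **Early sampling during prior therapy is nowhere stated.** This is right. A reader might infer that the plan allows a baseline draw on active treatment. In fact it only fails to prevent one. The 7-day overlap needs a sample at the edge of the screening window and registration on the first permitted day. Consent must come first, and both calendars and Appendix B place the sample under screening or baseline. The long off-drug interval needs none of this: it passes half of the total as soon as the sample is more than 14 days before first dose.

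**The lead-in sentence is narrow.** It concerns key pathways and sits with the tumor samples; the paired-difference definition is a separate, general statement. This stands. The point is strongest for the biopsies, and reaches the blood markers through the general definition.

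**The analysis is descriptive and meant to show feasibility.** This also stands, and it limits the consequence. A descriptive change offered as a guide for larger trials still has to be attributable to something.

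**The interval can be reconstructed.** Appendix B has containers labelled with collection date and time, and prior medication is reviewed at screening. That makes reporting by interval cheap. The plan does not ask for it.

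**Flexible timing is reasonable for optional biopsies in a phase I trial.** This is a fair argument against discarding pairs, and the fix below keeps them all.

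**Conclusion.** The point holds as a design weakness in a secondary, descriptive analysis. The baseline research sample has no earliest date and no link to the end of prior therapy or steroids, so the one contrast that isolates trigriluzole from the PD-1 antibody can mix off-drug time and recovery with the drug effect. At the screening limit 75% of the interval is off drug; at a Week -2 pre-dose draw none is. The 7-day overlap rests on study entry meaning registration.

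A reader might go on to infer that the paired difference would be mostly washout. The documents do not support that. The 75% is a share of elapsed time, not of marker change, and a majority share needs a recovery shift larger than a drug effect that is not given. Melanoma and high-PD-L1 lung cancer patients enrolled without earlier treatment have no cancer therapy to wash out, although lag and steroid exposure can still differ among them. The MTD/RP2D, the DLT rules and the planned 12–27 subjects are not affected.

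**What to change.** In section 1.3.3, in both sampling paragraphs of section 1.8 and in footnote 5 of both calendars, replace the open-ended timing with: *after the end of prior therapy and its 3-week washout, and no more than 14 days before the first dose*. Where no baseline biopsy is taken, or where it is taken that day, draw the baseline blood with the Week -2 pre-dose PK sample, which is already scheduled.

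If study entry is registration, any sample drawn between registration and first dose meets both conditions: the washout is then complete and the gap is at most 14 days. The protocol should state that meaning of study entry.

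In section 6.1, add that sample date and days since last therapy or steroid are recorded for every pair, that all pairs are kept, and that the Baseline vs. Week 1 change is reported with out-of-window pairs flagged and summarised separately.

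Cost: tighter scheduling of some baseline biopsies, and less room for the preferred 3–14-day gap between blood and biopsy. No extra visit is needed. At the outer edge of the window half the interval is still off drug, so the recorded lag should be shown beside the results.
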